6.2.6. Prior and Subsequent Anti-cancer Therapy

All verbatim terms collected of prior and subsequent anti-cancer therapy will be coded to Anatomical Therapeutic Classification (ATC) and PT using the WHO-DD Version Sep2017.

The prior and subsequent anti-cancer therapy will be summarized separately by presenting the number and percentage of patients by PT and ATC. Patients taking the same medication multiple times will only be counted once for that PT or ATC. Each summary will be ordered by descending order of incidence of ATC class and PT within each ATC class. The data will be presented in a patient listing.

For subsequent anti-cancer therapy, if the term contains the word “RADIATION”, the therapy will be classified to radiotherapy; it is classified as systemic anti-cancer therapy unless the therapy can be grouped to surgery. The number and percentage of randomized patients receiving subsequent anti-cancer therapy will be provided by systemic anti-cancer therapy (by drug name and by line), radiotherapy, and surgery. All subsequent anti-cancer therapies will be presented in a patient listing.

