ICH	International Conference on Harmonization
IRB	institutional review board
IV	intravenous
IWRS	interactive web-response system
LD	longest diameter

Abbreviation	Definition
LDH	lactate dehydrogenase
LS	least square
M	mitosis phase of cell cycle
MATE1 or 2-K	multidrug and toxin extrusion 1 or 2-K
MDR1	p-glycoprotein
MedDRA	Medical Dictionary for Regulatory Activities
MHRA	Medicines and Healthcare Products Regulatory Agency
MRI	magnetic resonance imaging
MRP1 or 2	multidrug resistance protein 1 or 2
NCI	National Cancer Institute
NCI-H69	human small cell lung cancer cell line
NE	not evaluable
NYHA	New York Heart Association
OAT1 or 3	organic anion transporter 1 or 3
OATP1B1 or 1B3	organic anion transporting polypeptide 1B1 or 1B3
OCT1 or 2	organic cation transporter 1 or 2
PCI	prophylactic cranial irradiation
PD	progressive disease
PET	positron emission tomography
PFS	progression-free survival
PK	pharmacokinetic(s)
PK/PD	pharmacokinetic/pharmacodynamic
PP	per protocol
PR	partial response
PRO	patient-reported outcome
QOL	quality of life
Rb	retinoblastoma protein
RB-1	retinoblastoma gene
RBC	red blood cell
RECIST	Response Evaluation Criteria in Solid Tumors
RH	relative humidity
RNA	ribonucleic acid
RNASeq	RNA sequencing
S	synthesis phase of cell cycle in which DNA is replicated
SAE	serious adverse event
SAP	statistical analysis plan

Abbreviation	Definition
SCLC	small cell lung cancer
SD	stable disease
SMC	safety monitoring committee
SOP	standard operating procedure
$t_{1/2}$	terminal half-life
$T_{max}$	time to reach $C_{max}$
TP53	tumor protein 53
UGT1A1	uridine disphosphate glucuronosyltransferase 1 family, polypeptide A1
ULN	upper limit of normal
$V_z$	volume of distribution in the terminal elimination phase
WBC	white blood cell
WHO	World Health Organization

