### **8.8. Prophylactic Cranial Irradiation**

Prophylactic cranial irradiation for patients without detectable brain metastases has been shown to decrease the frequency of subsequent intracranial relapse and improve survival for patients with SCLC ([Aupérin A 1999](#); [Slotman 2007](#)). Therefore, patients with a confirmed CR are strongly encouraged to receive PCI after completion of chemotherapy. Patients with a confirmed PR should also consider PCI after completion of chemotherapy based on the investigator's judgment.

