#### **10.7. Survival Follow-up Phase**

Monthly phone calls will be made to each patient that is in the long-term Survival Follow-up Phase. Patients will be followed for survival at a minimum until 50% of the patients randomized to Part 2 of the study have died. In addition, for patients who have not had disease progression at the time of study drug discontinuation, tumor assessments, including all sites of disease, will be assessed radiologically by CT or MRI, as performed at screening,

every 2 months (approximately  $60 \pm 7$  days) until the occurrence of progressive disease or study completion.

The following information will be collected monthly for all patients:

- Survival status
- Details of any anticancer treatment

The following additional information will be collected at  $60 \pm 7$  days after the Post-Treatment Visit (**Part 2 only**):

- Immunologic markers blood sample collection
- Hematology sample collection

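### Read literally, the text match in SAP 6.2.6 would count subsequent therapies recorded as 'radiotherapy' or 'PCI' as systemic therapy

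*SAP*

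**What the plan says.** SAP 6.2.6 (Prior and Subsequent Anti-cancer Therapy) handles subsequent therapy in three steps.

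- **Coding.** "All verbatim terms collected of prior and subsequent anti-cancer therapy will be coded to Anatomical Therapeutic Classification (ATC) and PT using the WHO-DD Version Sep2017".
- **Classification.** "if the term contains the word “RADIATION”, the therapy will be classified to radiotherapy". After a semicolon comes the rule for the rest: "it is classified as systemic anti-cancer therapy unless the therapy can be grouped to surgery". The word 'otherwise' is missing, but the second clause makes sense only as the default for terms that fail the first.
- **Output.** The number and percentage of randomized patients "will be provided by systemic anti-cancer therapy (by drug name and by line), radiotherapy, and surgery". All subsequent therapies are also listed by patient.

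For this step the SAP gives no synonyms, abbreviations, case report form category or medical review. It does not say whether the term searched is the verbatim or the coded one.

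On the protocol side, section 8.8 says that "patients with a confirmed CR are strongly encouraged to receive PCI after completion of chemotherapy" and asks that PCI be considered after a confirmed PR. The abbreviation list expands PCI as "prophylactic cranial irradiation". During survival follow-up, section 10.7 collects each month "Details of any anticancer treatment".

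**The concern.** A single-word match with a default to systemic therapy is only as good as the match between that word and what sites write. Two of the likeliest entries fail it. 'Radiotherapy' is what the SAP itself calls the class in 6.2.6 and the prior-therapy item in 6.2.3, and the protocol uses it in exclusion criterion 10. 'PCI' is the protocol's usual short form for a treatment it tells investigators to expect. With up to 80 centers in North America and Europe (Protocol 7.1), mixed wording is foreseeable.

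At stake is the accuracy of one descriptive table. That table has a use, because SAP 5.2.8 does not censor OS at later anti-tumor treatment and SAP 6.2.8.8 compares OS between the Part 2 arms. A reader who asks whether post-study treatment differed between arms will look there. PCI advice follows response, so misfiled entries need not balance across arms if response differs. A radiation course shown under a drug-name and line breakdown is also wrong on its face.

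**Working it through.** There is no plan figure to reproduce. The check applies the rule as written to plausible terms.

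**Inputs.** The trigger word and the default come from SAP 6.2.6. The test terms are assumptions, since the documents contain no recorded entries. Because containing a word can be programmed in two ways, both are shown.

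| Term | Substring match | Whole-word match | Class under the rule |
|---|---|---|---|
| RADIATION; RADIATION THERAPY | yes | yes | radiotherapy |
| PROPHYLACTIC CRANIAL IRRADIATION | yes | no | radiotherapy or systemic, depending on programming |
| RADIOTHERAPY; WHOLE BRAIN RADIOTHERAPY; PALLIATIVE RADIOTHERAPY | no | no | systemic |
| PCI; WBRT; SBRT; THORACIC XRT | no | no | systemic |
| STEREOTACTIC RADIOSURGERY; GAMMA KNIFE | no | no | systemic or surgery; the SAP does not say |

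**Effect on the table.** The summary counts patients, not entries. A patient whose only radiation entry fails the match drops out of the radiotherapy row. The same patient is added to the systemic row only if no systemic drug is recorded for them. The drug-name breakdown gains a row that is not a drug.

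**Does the class feed any other analysis?**

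- BOR (SAP 5.2.6.4) stops at subsequent anti-cancer therapy, whatever its class.
- PFS (SAP 5.2.7 and Table 18) is censored at new anticancer treatment, whatever its class.
- OS (SAP 5.2.8) is not censored for later treatment.

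None of the three depends on the radiotherapy, systemic or surgery label.

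**Size.** The number misfiled is the number of radiation entries multiplied by the fraction worded so as to miss the match. The documents give neither. If 10% to 40% of an arm of 35 had later radiotherapy or PCI (an assumption with no source in the documents), then 35 × 0.10 = 3.5 and 35 × 0.40 = 14, so about 4 to 14 patients per arm would have an entry exposed to the rule. That is a ceiling on exposure under the assumption. The misfiled count lies anywhere from zero up to it.

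**The case against.** The strongest reply is that the rule may work well on the actual data. The protocol also writes 'radiation therapy' (exclusion criterion 2 and section 8.6), which matches under either reading, and PCI written out contains the string. Other SAP rules look fitted to collected entries, for example the allowance for IVPB as a specified route in 5.1.1.6, so the upper-case RADIATION may be too. The search may run on a coded term. PCI may be recorded elsewhere, since Protocol 8.6 separately requires therapeutic procedures to be documented. A row labelled PCI among drug names would be conspicuous, the listing would expose it, and SAP 6.1.1 requires independent program validation and checks of tables against listings.

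Much of this stands. It rules out saying that entries have been misfiled, or how many. It does not repair the rule. Validation against the plan would confirm a program that follows the plan's wording, and nothing in the SAP says that sites' entries were reviewed before the word was chosen. Elsewhere the SAP is more careful: it uses preferred-term lists for infections (Table 4), several named terms for mucositis (5.1.2.2), and a list plus medical review for hematologic hospitalizations (5.1.1.11 and Table 6).

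A reader might infer that radiotherapy and PCI are in fact being counted as systemic lines. That would need three things the documents do not show: sites used those words, the verbatim term is searched, and PCI is entered as subsequent therapy. A reader might also infer that line numbers shift. The SAP does not say whether line is collected or derived, so this cannot be shown.

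**Conclusion.** The point holds as a conditional one. The stated rule gives the wrong class for any entry worded 'radiotherapy' or 'PCI', and an implementation-dependent class for spelled-out 'irradiation'. This is a defect in a stated rule, not merely a missing detail, because the default actively sends those entries to systemic therapy. Its extent is undetermined, and the 4 to 14 per arm above must not be quoted as a misfiling estimate.

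It is a minor matter. Only the descriptive by-arm table of subsequent therapy is affected. It would be a mistake to read it as a threat to the PFS, BOR or OS results, which ignore the class. The conclusion assumes that the rule is programmed literally and that the field searched keeps the site's wording.

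**What to change.** In SAP 6.2.6:

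1. Insert the missing 'otherwise' and state whether the verbatim or the coded term is searched.
2. Classify from a therapy-type field if the case report form collects one. If not, use a radiotherapy term list fixed before unblinding: radiation, radiotherapy, irradiation, PCI, WBRT, SBRT, XRT, radiosurgery and similar.
3. Send terms that match no list to medical review without reference to treatment arm, in place of the systemic default. SAP 6.2.12 unblinds at the final analysis and reports an end-of-study analysis later, so review cannot all precede unblinding. Terms recorded afterwards should go through the same review, with arm withheld from the person classifying.
4. Count lines over systemic drugs only, and say how line is derived.

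The cost is a few sentences, a short term list, and review of the unmatched entries. No data collection or estimate changes.

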6.2.7. Efficacy Analyses

All the efficacy variables will be summarized using descriptive statistics by cycle or visit, with the supportive data provided in patient listings. Part 1 will be summarized using only descriptive statistics. For Part 2, in addition to the descriptive summary, the between treatment comparison (trilaciclib vs placebo), if applicable, will be performed only for those prospectively-defined endpoints outlined in [Section 5.1.1](#). For these comparisons, all statistical tests will be conducted at a two-sided significance level of 20% unless otherwise specified. Where appropriate, model-based point estimates, together with their two-sided 80% CIs will be presented along with the two-sided p-value for the test. Graphical presentation of efficacy results will be appropriately performed as needed.

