### **13.4. Efficacy Analysis**

#### **13.4.1. Efficacy Endpoints**

Unless otherwise stated, the terminology ‘hematologic parameters’ refers to ANC, lymphocyte, hemoglobin, and platelet counts; the terminology ‘hematologic toxicities’ refers to neutropenia, lymphopenia, anemia, and thrombocytopenia. Each parameter and toxicity will be evaluated individually, but are described as such to avoid repetition. Hematologic toxicities are assigned based on CTCAE, Version 4.03.

- Hematologic kinetic endpoints:
  - Change and percent change in hematologic parameter values from baseline to the Post-Treatment Visit
  - Change and percent change in hematologic parameter values from predose for a particular cycle to the end of that cycle
  - Change and percent change in hematologic parameter values from predose for a particular cycle to nadir for that cycle
  - Rate of change in hematologic parameter values from predose for a particular cycle to nadir for that cycle
  - Change and percent change in hematologic parameter values from nadir for a particular cycle to the end of that cycle
  - Rate of change in hematologic parameter values from nadir for a particular cycle to the end of that cycle
  - Area under the curve in hematologic parameter values from predose for a particular cycle to the end of that cycle
  - Area under the curve in hematologic parameters from predose for a particular cycle to nadir for that cycle
  - Area under the curve in hematologic parameter values from nadir for a particular cycle to the end of that cycle
  - By cycle and overall study hematologic parameter nadir values
  - Time to hematologic parameter value nadir by cycle
  - Time to return to predose hematologic parameter values by cycle
  - Proportion of patients with a return to predose hematologic parameter values by cycle
- Hematologic toxicity endpoints:
  - Incidence of Grade 3 and 4 hematologic toxicities
  - Total number of Grade 3 and 4 hematologic toxicities
  - Proportion of patients with a hematologic toxicity recovery by cycle
  - Time to hematologic toxicity recovery by cycle

- Chemotherapy exposure and compliance endpoints:
  - Duration on treatment
  - Number of cycles received
  - Dose intensity and cumulative dose
  - Incidence of dose interruptions, delays, and reductions
  - Incidence of dose delays due to hematologic toxicity
  - Incidence of study treatment termination due to hematologic toxicity
  
- Other efficacy endpoints:

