#### 13.4.2.2. Analysis of Hematologic Toxicity Endpoints

The number and percentage of patients with Grade 3 and 4 hematologic toxicities at each cycle and overall during the Treatment Phase will be tabulated for each type of hematologic toxicity and across all type of hematologic toxicities. Percentages for by-cycle summaries will be based on the number of patients treated in the cycle. For tabulations performed based on data collected in Part 2, the difference in rates between treatment groups will be calculated. Two-sided 95% CIs will be constructed around the difference in treatment groups. If there are substantial dose reductions, an incidence rate, adjusting for cumulative exposure, may be reported to account for differing amount of exposure by cycle.

The total number of Grade 3 and 4 hematologic toxicities will be summed over the entire Treatment Phase per patient, separately for each type of hematologic toxicity and across all types of hematologic toxicities. To account for differing amount of exposure, a toxicity rate will be calculated for each patient, and defined relative to cumulative exposure (total number of toxicities divided by cumulative exposure). A recurrent events model may be performed to estimate the incidence of Grade 3 or higher hematologic toxicities and test for the difference between treatment groups.

For each hematologic parameter and cycle, the following shift summaries will be performed: from predose toxicity to maximum ontreatment toxicity; from predose toxicity to end of cycle toxicity; from maximum postdose toxicity to end of cycle toxicity.

Hematologic recovery will be defined in the SAP. The number and percentage of patients with hematologic recovery will be calculated at each cycle. Time to postdose recovery within a cycle will be estimated using the Kaplan-Meier method. A Cox proportional hazard model adjusted for baseline hematologic toxicity and ECOG will also be performed.

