2. STUDY DETAILS

2.1. Study Objectives

The primary, secondary, and exploratory objectives of this study are presented in [Table 1](#).

Table 1 G1T28-02: Study Objectives

	Phase 1b Dose-Finding Portion of Part 1	Phase 2a Expansion Portion of Part 1	Phase 2a Part 2
Primary Objectives			
Assess the DLTs and define the Phase 2 dose of G1T28 administered with E/P therapy	X		
Assess the safety and tolerability of G1T28 administered with E/P therapy	X	X	X
Secondary Objectives			
Assess the PK profile of G1T28	X		
Assess the PK profile of etoposide and carboplatin when administered with G1T28	X		
Assess the hematologic profile (kinetics and incidence/duration/frequency of toxicities) of G1T28 administered with E/P therapy	X	X	X
Assess the incidence of febrile neutropenia	X	X	X
Assess the incidence of infections	X	X	X
Assess the utilization of RBC and platelet transfusions	X	X	X
Assess the utilization of hematopoietic growth factors	X	X	X
Assess the utilization of systemic antibiotics	X	X	X
Assess the incidence of chemotherapy dose reductions and dose interruptions overall	X	X	X
Assess the incidence of Grade 2 or greater nephrotoxicity	X	X	X
Assess tumor response based on RECIST, Version 1.1	X	X	X
Assess PFS and overall survival	X	X	X
Exploratory Objectives			
Assess the incidence of mucositis	X	X	X
Assess the incidence of alopecia	X	X	X
Assess the incidence of fatigue	X	X	X
Assess patient-reported QOL	X	X	X
Assess immunologic markers			X

DLT = dose-limiting toxicity; E/P therapy = etoposide + carboplatin on Day 1 and etoposide on Days 2 and 3 of 21-day cycles; PFS = progression-free survival; PK = pharmacokinetic; QOL = quality of life; RBC = red blood cell; RECIST = Response Evaluation Criteria in Solid Tumors

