6.2.8.2. Laboratory Evaluations

For hematology and clinical chemistry labs the observed values and change from baseline will be summarized for each visit during the treatment period using descriptive statistics.

Toxicities for clinical labs will be characterized according to CTCAE, Version 4.03 ([Table A-1](#) of Appendix when possible), and the frequency and percentage of patients with each CTCAE grade for each visit during the treatment period will be described. Moreover, any occurrence of

grade 3 or grade 4 during the treatment period will be summarized, and shift in grade from baseline to the worst post-baseline value will be summarized. Both the scheduled and unscheduled assessments will be used to identify the worst post-baseline values.

Listings of all laboratory data, its normal reference ranges, and its CTCAE grade (when possible) will be provided.

6.2.8.3. **Vital Signs**

For vital sign parameters Systolic Blood Pressure, Diastolic Blood Pressure, Pulse Rate, Temperature, Weight, the observed values and change from baseline will be summarized using descriptive statistics at each visit during the treatment period.

Additionally, the frequency and percentage of patients with any potentially clinically significant findings (defined in [Table 11](#)) during the treatment period will be presented. A listing of all vital sign data will be provided.

6.2.8.4. **Performance Status**

Descriptive statistics will be presented for ECOG score for the observed values and change from baseline. A listing of ECOG score for all patients will be provided.

6.2.8.5. **Physical Examination**

A listing of physical examination findings for all patients will be provided.

6.2.8.6. **ECG**

Descriptive statistics will be presented for each ECG parameter for the observed values and change from baseline to post baseline. A listing of all ECG data will be provided.

The criteria of potentially clinically significant findings are defined in [Table 13](#). The frequency and percentage of patients with any potentially clinically significant findings during the treatment period will be presented. The supportive data will be provided in patient data listings.

6.2.8.7. **Analyses of Objective Response**

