- Calculation and analysis of incidence rate of hematologic toxicity, adjusting for cumulative exposure
- Calculation and analysis of toxicity rate relative to cumulative exposure (total number of toxicities divided by cumulative exposure).
- Recurrent events model estimating the incidence of Grade 3 or higher hematologic toxicities and testing for the difference between treatment groups.
- For each hematologic parameter and cycle, the shift summaries of the following:
 - From predose toxicity to maximum on treatment toxicity;
 - from predose toxicity to end of cycle toxicity;
 - from maximum postdose toxicity to end of cycle toxicity.

Protocol Section 13.3.2.4 (Other Efficacy Endpoints)

- The number and percent of infections summarized by maximum severity
- The infection rate: The number of infections occurring during the Treatment divided by cumulative exposure.
- ANOVA on FACT scores
- The association between composite endpoints and BOR, OS, and PFS

Protocol Section 13.5 (Exploratory Analyses)

The analysis in the section is not covered in the SAP

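### The SAP omits, and does not list as removed, the protocol's between-arm difference (95% CI) in Grade 3 and 4 hematologic toxicity rates; lymphopenia, thrombocytopenia and neutropenia incidence lose most.

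*SAP*

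**What the plan says.** **Protocol.** A secondary objective, which applies to Part 2 and is repeated in SAP 2.1, is to "Assess the hematologic profile (kinetics and incidence/duration/frequency of toxicities) of G1T28 administered with E/P therapy". Section 13.4.1 turns this into efficacy endpoints, among them "Incidence of Grade 3 and 4 hematologic toxicities", with neutropenia, lymphopenia, anemia and thrombocytopenia each evaluated individually. Section 13.4.2.2 tabulates these patients by cycle and overall, for each type and across types. For Part 2 it says "the difference in rates between treatment groups will be calculated. Two-sided 95% CIs will be constructed around the difference in treatment groups". That wording is unconditional. The model in the same section is optional: "A recurrent events model may be performed to estimate the incidence of Grade 3 or higher hematologic toxicities". The section also plans a recovery proportion by cycle, a Kaplan-Meier time to recovery and a Cox model, and leaves the definition of recovery to the SAP.

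**SAP.** Section 6.2.7 states that "the between treatment comparison (trilaciclib vs placebo), if applicable, will be performed only for those prospectively-defined endpoints outlined in" Section 5.1.1. Grade 3/4 occurrence appears in 6.2.8.2 as a laboratory safety result, where the planned tabulation reads "grade 3 or grade 4 during the treatment period will be summarized, and shift in grade from baseline to the worst post-baseline value". Section 6.2.8 plans no inference on safety data unless otherwise specified. Section 7, whose purpose is to list what was removed, includes for hematologic toxicity "Calculation and analysis of incidence rate of hematologic toxicity, adjusting for cumulative exposure", the per-exposure toxicity rate, the recurrent-events model with its test, and the shift summaries.

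**The concern.** SAP Section 4 states the hypothesis as preservation of every hematopoietic lineage, and names lymphocytes. How many patients in each arm reach Grade 3 or 4 in each lineage is the most direct summary of that hypothesis, and the incidence part of the objective asks for it. The protocol promised an estimate of the difference with its uncertainty. Under the SAP, readers will have two percentages in a safety table and no interval. They will also have a Section 7 list from which they could reasonably conclude that the unadjusted difference had been kept. In a trial sized on clinical rather than statistical grounds, the interval is what stops a reader from over- or under-reading a gap between two percentages based on about 35 patients each.

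**Working it through.** **1. Text comparison.**

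| Protocol 13.4.2.2 item | In SAP 6.2.7.1? | In SAP Section 7 list? |
|---|---|---|
| Grade 3/4 rate difference with 95% CI, by type and across types | No | No |
| Exposure-adjusted incidence rate | No | Yes |
| Per-exposure toxicity rate | No | Yes |
| Recurrent-events model (optional) | No | Yes |
| Toxicity shift tables | No | Yes |
| Recovery proportion by cycle | No | No |
| Time to recovery | Neutrophils only, as duration of neutropenia | No |

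The eight binary variables in 6.2.7.1 are febrile neutropenia, RBC transfusion, platelet transfusion, GCSF, ESA, IV antibiotic, infection SAE and pulmonary infection SAE. Grade 3/4 incidence accounts for 0 of these 8. The unadjusted rate difference accounts for 0 of the 4 hematologic-toxicity removals in Section 7. The return-to-predose items that Section 7 also lists are separate protocol endpoints, not toxicity recovery.

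**2. What is compared, by lineage** (grade limits from SAP Table A-1).

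- *Neutrophils:* febrile neutropenia and duration of Grade 4 and Grade 3/4 neutropenia. Sections 5.1.1.8 and 5.1.1.9 derive each patient's number of cycles with such an event, but 6.2.7.1 compares only duration.
- *Red cells:* actual transfusion or Hb < 8.0 g/dL. The Grade 3 limit is also < 8.0 g/dL, and the table has no Grade 4 level for hemoglobin. Every patient with lab-based Grade 3 anemia in the treatment period is therefore already an event, together with patients transfused above that level.
- *Platelets:* actual transfusion or a count ≤ 10 × 10⁹/L. Grade 3 starts below 50 and Grade 4 below 25, so a patient with a count between 10 and 50 who is not transfused is a Grade 3 or 4 case but not an event here.
- *Lymphocytes:* mean count over time is a prospectively defined analysis, but 6.2.7.1 gives it only descriptive statistics and graphs. The ANCOVA and repeated-measures models are declared removed in Section 7, so no between-arm estimate remains.
- *Composite:* time to first MAHE includes dose delay or reduction due to ANC or platelet counts and hospitalization for hematologic events, but it isolates no lineage.

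**3. Size of the missing interval.** Inputs: n = 35 per arm (Protocol 13.1), unstratified, all randomized patients dosed.

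The plan's own figure first. The Wilson half-width is z·√[p(1−p)/n + z²/(4n²)] / (1 + z²/n). At p = 0.5 and z = 1.96 this is 1.96 × √(0.007143 + 0.000784) / 1.1098 = 0.1572, against the stated 0.157. For means, t(0.975, 34)/√35 = 0.3435, against the stated 0.344. Both reproduce.

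For a difference, the Newcombe interval combines the two Wilson intervals. Its half-width (half the interval's length) is largest with both rates near 50%: √2 × 0.1572 = 0.222. The Wald half-width there is 1.96 × √(2 × 0.25/35) = 0.234. At the SAP's 80% level the Newcombe figure is 0.150.

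Taking equal rates in both arms across the ranges in Protocol 4.1, the 95% Newcombe half-widths are:

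| Toxicity | Assumed rate in both arms | Half-width |
|---|---|---|
| Neutropenia | 47% to 92% | 0.146 to 0.222 |
| Thrombocytopenia | 10% to 46% | 0.155 to 0.222 |
| Anemia | 7% to 34% | 0.142 to 0.213 |

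With unequal rates, assume 30% on placebo and 10% on G1T28. The difference is −20 points, and the 95% Wald half-width is 1.96 × √(0.21/35 + 0.09/35) = 0.181, giving about −38 to −2 points. At 80% it is 1.2816 × 0.0926 = 0.119, giving about −32 to −8. The confidence level chosen for a restored analysis therefore matters.

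**The case against.** The strongest reply is that little is lost. Any occurrence of Grade 3 or 4 is tabulated by treatment group, graded AE summaries and a pooled hematologic-toxicity AE table (which includes lymphopenia) are planned, and the difference is then a subtraction. Protocol 13.2.3 calls the study descriptive with no formal hypothesis testing. SAP 6.2.7 states its restriction openly, and Section 7 does declare the only between-arm test that 13.4.2.2 offered for this endpoint. Related endpoints are compared, and duration of neutropenia is in effect time to neutrophil recovery.

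Much of this stands, and it limits the point. A reader might infer that Grade 3/4 incidence has been dropped, that no lineage is compared, or that Section 7 is silent on hematologic toxicity altogether. The documents support none of these: the counts remain, anemia has a close proxy, actual platelet transfusions count at any platelet level, and four related removals are declared. A reader might also take the Protocol 4.1 ranges as expected Grade 3/4 rates on this regimen. They carry no grade, cover etoposide with cisplatin or carboplatin, and give no lymphopenia figure.

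Three things do not fall away. A difference with a CI is an estimate, so it is compatible with the no-testing statement, and the protocol promised both together. A subtraction supplies no interval. And the SAP gives lymphopenia no proxy.

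**Conclusion.** The point holds in a limited form. What is missing, and not declared as removed, is the unadjusted Part 2 difference in Grade 3 and 4 hematologic toxicity rates with its two-sided 95% CI. The gap is sharpest for lymphopenia, which has no between-arm estimate, then for Grade 3/4 thrombocytopenia and for neutropenia incidence. It is small for anemia. The recovery proportion, and time to recovery for lineages other than neutrophils, are likewise neither defined nor declared removed.

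The restored interval would have a half-width of at most about 0.22 at 35 per arm. It would inform the reader without being decisive. That figure assumes all randomized patients are dosed and ignores stratification; the rate-specific widths and the 30% versus 10% example are illustrations only.

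One limit concerns the word undeclared. Section 7 is written against Protocol Amendment 7, while SAP Section 1 says the SAP is based on Version 8. Amendment 7 is not among the documents, so whether the rate difference stood in it cannot be checked. Against the current protocol it is not listed. The matter should be settled before unblinding, but it does not threaten the trial's primary safety objective.

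**What to change.** Before unblinding:

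1. Add to the binary list in SAP 6.2.7.1 the lab-based occurrence during the treatment period, in the FAS, of Grade 4 neutropenia and of Grade 3/4 neutropenia, anemia, thrombocytopenia and lymphopenia. Use the ECOG-stratified difference already specified there, but with the protocol's two-sided 95% CI in place of that section's 80% CI, and report the results as estimates.
2. List in Section 7, with a reason, the recovery endpoints and any by-cycle or across-type differences that will not be produced, and align the list with Protocol Version 8.

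The grading already exists for 6.2.8.2 and the stratified program for 6.2.7.1, so the work is a few table rows. The downside is more comparisons without multiplicity adjustment. The anemia row will overlap heavily with the RBC transfusion endpoint, but it completes the set. If the sponsor prefers not to add these rows, listing the removal with a reason in Section 7 would settle the declaration problem, though lymphopenia would still have no between-arm estimate.
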